**Transcranial Photobiomodulation for
reducing autism symptoms in
children.**

October 1, 2020

PROTOCOL TITLE:

Transcranial photobiomodulation for reducing autism symptoms in children.

PRINCIPAL INVESTIGATOR:

Name	[name]
Department	N/A
Phone Number	

CO-INVESTIGATORS:

Name	[name]
Department	N/A
[contact]

Name	[name], CFA, Esq.
Department	N/A
[contact]

1.0 Purpose of the study:

The purpose of this 8-week open label feasibility study is to assess the tolerability, safety and efficacy of Transcranial LED Therapy for language learning and reducing symptoms of autism in children.

The investigators propose to enroll up to 30 participants of both genders ages 24 months to 6 years who have been previously diagnosed with moderate to severe ASD by licensed professionals according to the Diagnostic and Statistical Manual of Mental Disorders, Fifth Edition (DSM-5) criteria for Autism Spectrum Disorder (ASD).

The hypothesis to be tested is that exposure to photobiomodulation and speech parsing program will reduce children's symptoms of autism, such as delays in language production and comprehension, anxiety, tantrums, limited eye-contact and improve responsiveness.

2.0 Background / Literature Review / Rationale for the study:

2.1 Background Science of Photobiomodulation and Rationale:

There are several studies that suggest that mitochondrial energy disturbance is an underlying mechanism of autism, for at least some of the children. Specifically, Weisman, Kelley, Bauman, Cohen, Murray, Mitchell and Kern (2008) looked at the medical records of 25 children diagnosed with autism and found that "Levels of blood lactate, plasma alanine, and serum ALT and/or AST were increased at least once in 76%, 36%, and 52% of patients, respectively". Furthermore, 2 out of those 25 people had rare mtDNA mutations. The authors concluded that at least for a subset of ASD children, mitochondrial disturbances in energy production could be the underlying mechanism. Furthermore, Giulilvi, Zhang, Omanska-Klusek, Ross-Intra, Hertz-Picciotto, Tasson and Pessach (2010), looked at biochemical markers of ASD kids (2-5yo), and concluded that ASD children are more likely to have Mitochondria dysfunction, mtDNA replication and mtDNA deletion than neurotypical ones.

In addition, Siddiqui, Elwell and Johnson (2016) conducted meta-analyses of the studies reporting decreased activity of mitochondrial electron transport chain (ETC) complexes and reduced gene expression of mitochondrial genes, in particular genes of respiratory chain complexes, in individuals with autism (not necessarily children). They concluded that current research supports the link between ASD and mitochondrial dysfunction. However, they also conceded that in many studies that they reviewed the sample size was small and argued for further research including near infrared spectroscopy to provide more precise information of Mitochondria dysfunction in ASD individuals. Based on these and other studies, it is reasonable to conclude that there is evidence linking ASD with mitochondria dysfunction (specifically difficulties with energy producing) in at least some ASD individuals.

Transcranial photobiomodulation (tPBM) could be the solution to Mitochondrial Disturbances in ASD individuals (resulting in functional brain connectivity): Michael Hamblin (2016) argued that Transcranial Photobiomodulation (“tPBM”) could be helpful in addressing various neurological disorders (including ASD) because Nitric Oxide could be dissociated by photons of light. When Nitric Oxide is dissociated, the mitochondrial membrane potential is increased, more oxygen is consumed, more glucose is metabolized and more Adenosine Triphosphate (ATP) is produced by the mitochondria. In another paper, [name] discusses research on the effect of light stimulation on mitochondria, specifically he discusses in vitro studies with isolated mitochondria (isolated rat livers), where increased ATP synthesis was detected. Furthermore, tPBM has been found to be effective in treating several neurological conditions and disorders, including Stroke (Naeser and Hamblin, 2011), Traumatic Brain Injury (Naeser and Hamblin, 2015; Naeser et al, 2016) and Alzheimer’s Disease (Johnston et al, 2015).

We are developing a safe and effective protocol for administering tPBM via a wearable device. This physical device is getting developed by JelikaLite LLC. The parameters are developed by [name] (the PI of this study), [name] (leading photobiomodulation expert from Harvard Medical School and an advisor to JelikaLite), [name] (leading neuroscientist who is studying photobiomodulation at Boston Medical University and an advisor to JelikaLite), and [name] (an industrial product designer with over 30 years of expertise in designing medical devices). The purpose of this feasibility study is to evaluate the safety and comfort of the product, as well as preliminary efficacy of the treatment effect. The device will stimulate Default Mode Network (to increase brain connectiveness) as well as Broca and Wernike areas (to facilitate speech comprehension and production) and Occipital lobe (as many ASD children rely on visual information for language learning). The device will be physically light, comfortable to wear for children and could eventually be used at home as frequently as necessary.

The reason why the device may be helpful to children is because of the science of photobiomodulation. The device will have embedded LED lights in it, which will shine red light and near infra red lights. The children will wear the device for approximately 5-10 minutes, twice a week (closely replicating the protocol of Leisman et al as well as the clinical study at MGH). The light stimulates mitochondrial ATP production. Only about 2% of the light penetrates the skull. However, because brain is the largest energy consuming organ of the body, even those 2% result in significant

improvement of the symptoms (even small boost in ATP production results in significant improvement). Having more energy enables the brain cells to heal, grow and form new neural connections. Other benefits of tPBM is increased blood flow to the brain, which increase brain oxygen supply and reduce inflammation.

3.0 Safety of the Device

We are asking the Board to make a non-significant risk determination.

The device is not approved or marketed.

The device does not pose a risk to participants under 21 CFR 812.3(m).

This investigational device is not:

- Intended as an implant and presents a potential for serious risk to the health, safety or welfare of a participant;
- Purported or represented to be for use supporting or sustaining human life and presents a potential for serious risk to the health, safety or welfare of a participant
- For a use of substantial importance in diagnosing, curing, mitigating or treating disease or otherwise preventing impairment of human health and presents a potential for serious risk to the health, safety or welfare of a participant or
- Otherwise presents a potential for serious risk to the health, safety or welfare of a participant.

Please see Response to January 15 New England IRB Letter, specifically Responses to Questions 5 and 6, for a full explanation of the device safety and comparison to other predicate devices. .

4.0 Inclusion and Exclusion Criteria:

Inclusion Criteria:

1. Male or female participants between 2 years and 6 years of age (inclusive), of all races.
2. Previously diagnosed with moderate or severe ASD by a licensed professional.

3. Participants may be receiving any behavioral intervention therapy (e.g., ABA, Floor Time) during the course of the treatment. The final statistical analysis will control for the participants receiving behavioral therapies in control and experimental conditions. We expect the majority of the participants in both control and experimental conditions to be receiving behavioral therapies. There is no known interactions or complications of tPBM with behavioral therapy.

4. Parents of participants must understand the nature of the study.
5. Parents of participants must sign an IRB- approved informed consent form before initiation of any study procedures.
6. Parents of participants must have a level of understanding sufficient to communicate with the investigator and study coordinator, and to cooperate with all tests and examinations required by the protocol.
7. Participant child experiencing a major psychiatric disorder will be allowed to participate in the study provided they do not meet any exclusionary criteria.
8. The participant child is willing to participate in this study.

Exclusion Criteria:

1. Participant child is experiencing severe self-injurious behavior or severe aggressive behavior to self or others (within past 7 days).
2. Participant has been diagnosed with another psychiatric or neurological disorder (e.g. epilepsy) or have exhibited symptoms of major psychiatric disorders within the last 30 days.
3. Participant has an unstable medical condition (that requires clinical attention).
4. Participant has a significant skin condition at the procedure sites (i.e., hemangioma, scleroderma, psoriasis, rash, open wound or tattoo).
5. Participant has an implant of any kind in the head (e.g. stent, clipped aneurysm, embolised AVM, implantable shunt - Hakim valve).
- 6. Participant has receiving medication on a regular basis for Autism or any other medical condition.**
7. Any use of light-activated drugs (photodynamic therapy) within 14 days prior to study enrollment (in US: Visudine (verteporfin) - for age related macular degeneration; Aminolevulinic Acid- for actinic keratoses; Photofrin (porfimer sodium) - for esophageal cancer, non-small cell lung cancer; Levulan Kerastick (aminolevulinic acid HCl) - for actinic keratosis; 5-aminolevulinic acid (ALA)- for non-melanoma skin cancer).
8. Current treatment with a psychotropic medication.
9. Investigator and his/her immediate family, defined as the investigator's child or grandchild.

5.0 Sample Size:

30 children will be included in the study. We need at least 15 participants in the control condition, and 15 participants will receive a combined light and audio treatment therapy. These numbers will allow us to gain sufficient statistical power to detect small size systematic effect. **We anticipate to screen about 40 participants to recruit 30 participants for the study.**

We plan to screen more than 30 prospective children, because we expect some of them to be ineligible for the study, due to the above listed Exclusion Criteria. We plan to enroll 30 children, so that each group will have at least 15 participants. We do anticipate that some of the participants will withdraw, for various reasons. participant We will continue screening until we have 30 enrolled participants.

If a participant drops out of the Study we will attempt to replace that participant, using the same Eligibility Screening Criteria.

6.0 Research Locations:

[name]

This is a private professional office, with a waiting room and a receptionist. There are several private rooms within the office.

The child will be led to a private room, which will have toys and books inside it. The caregiver and one of the researchers will be present in the room at all times.

[name]

This is a private professional office, with a waiting room and a receptionist. There are several private rooms within the office.

The child will be led to a private room, which will have toys and books inside it. The caregiver and one of the researchers will be present in the room at all times.

7.0 Procedures Involved:

7.1 Location: The study will use pre-test and post-test design. The entire study on the children will be done in the office. The weekly interview with the parent may be done either in office or by phone, as preferred by the parent.

7.2 Conditions: There are two conditions: placebo condition, and combined light and audio therapy treatment condition. The placebo control condition will listen to nursery rhymes. **The placebo control condition will wear the same device, however the lights are not going to be turned on. Otherwise, all experience for participants in control and experimental conditions will be identical.**

This study replicates and extends previous studies of photobiomodulation in children older than 5 years of age (Leisman et al, 2018).

7.3 Participants: The participants will be matched on age, gender and number of hours of therapy they receive independent from the study. The participants will be 24-71 month old children previously diagnosed with moderate or severe ASD. The experiment will use random assignment. We plan to use 30 participants (15 in each group). **We plan to screen about 40 participants (or fewer) to recruit the 30 participants for this study.**

7.4 Random Assignment: Random assignment will be achieved by using random number generator programs frequently used in research (such as random.org). Each participant is assigned a number. The list of 30 numbers is entered into the program, which creates a random sequence of 30 participants. Here is an example of the beginning of such list generated for 30 participants

1 – 23

2 – 25

1 – 12

2 – 15

1 – 21

2 – 5

1 – 19

2 - 9

Once the program generates the random sequence of 30 participants (in the example above, the sequence goes 23, 25, 12, 15, etc), we will simply alternate the assignment to treatment and control conditions. For example, in the example above, participant number 23 is assigned to the treatment condition (1), and participant number 25 is assigned to the control condition (2). Because the sequence of the participants is randomized, the assignment to conditions is random.

7.5 Treatment: The treatment will take place twice a week for up to 30 minutes at a time.

During the study, while participants will be wearing the photobiomodulation device, they will be listening to the audio program, and they may be playing with their parent or the experimenter, using the toys of their choice (out of the many available in the experimenter’s office). The caregivers will be present during the experiment at all times. When the child and the parent arrive, they will be welcomed to the office, and introduced to the toys.

The child will be encouraged to play with toys and interact with the parent (or the experimenter). The children in the experimental condition will be asked to wear the device for no longer than 15 minutes. The children in the controlled condition will play for 30 minutes and wear the same device, without turning it on (the device won’t be turned on at that time). The total time in the office will be about 30 minutes (including playing).

If the child becomes uncomfortable, the parents will be able to leave the experiment without any punishment. No coercion or deception is involved in this study.

7.6 Pre and Post-Testing: CARS2 will be used for pretest and post-test. Please see attached a sample CARS 2 test. CARS 2 scores will be compared for analyses. **In addition, EEG will be collected from the participants in both Control and Experimental conditions pre and post -treatment (before Starting treatment in session 1 and in the end of treatment of Session 8). Mobile FDA approved EEG device Brain Scientific will be used to collect children's pre and post test EEG. There is no known danger of EEG collecting. In this study it will be using for measuring the efficacy treatment only.**

7.7 On-going Data Collection: Parents will be asked to keep a daily diary of the child's behavior, specifically – words spoken, comprehension of instructions, eye contact, his sleep pattern, number of tantrums, anxiety, social interaction and eating. Qualitative data will be collected through short weekly interviews with the parents. These interviews can take place either in [name] office during the child's treatment or by phone. During those weekly interviews, the parents will be asked questions about their children's responsiveness to language, number of words they can produce, eye-contact, anxiety, frequency of tantrums, eating, and difficulties falling asleep and sleeping through the night. Please see attached proposed script for the weekly call. The qualitative data will be used to further inform and supplement quantitative data (total CARS 2 scores).

The study will collect qualitative and quantitative data. The quantitative data will be the total CARS2 scores of the participants of both Control and Treatment groups, obtained before and after the study is done. Mixed Design Analysis of Variance will be used to analyze quantitative data. **In addition, we will collect Before and After Prefrontal cortex EEG from the control and experimental treatment groups to measure electrophysiological changes in Prefrontal cortex. after treatment. EEG data will be analyzed (using Time-Frequency analysis), and after baseline normalization, the data will be used in aggregate to compare conditions numerically. The between group comparison before the treatment will be conducted using between subject T-test for each brainwave . The between group comparison will be conducted after treatment for each brain wave using between subject t-test. In addition, for the treatment condition only Before and After comparison will be conducted, using within subject t-test.** In addition, we will obtain qualitative data from weekly parental interviews, during which we will ask participants' parents about their children's behavior (see attached protocol). Qualitative data will be used for information purposes and will supplement quantitative data.

7.8 Blinding of the Researcher: [name] (the PI) will not be present in the room when the child is receiving the treatment. She will not be aware what group each particular participant has been placed in. [name] will be conducting the pre and post-testing interviews, as well as the on-going weekly interviews with the parents.

[name] will be present in the room when the child receives the treatment. However, [name] will not be doing the CARS testing, she will not be doing the weekly interviews, and she will not be doing the data analysis

Another professional (an independent contractor) will be analyzing the collected data at the end of the study, however, the individuals conducting the analysis will not have access to the private identifiable information and will not be aware about the specific group in which the individual participants have been placed.

Confidentiality: Participants' confidentiality will be protected by assigning them Study ID. The quantitative data will be analyzed and reported only as aggregate (averages and F scores). The qualitative data will be studied only by the researchers and, if reported for illustrative purposes only, it will be attached to the Study ID (not the identifying information). The participants will be asked for consent to report qualitative data with the Study ID.

8.0 Recruitment Methods:

We will put a flyer in both of [name] offices, informing patients of this potential study. We will also give this flyer to various therapists in Brooklyn and Manhattan who work with children on the autism spectrum (such as ABA therapists, speech therapists, etc.). We will also put up this flyer in centers and schools that provides ABA therapy and other therapy to children on the spectrum. (Please see attached proposed flyer).

Once a prospective parent contacts the researchers, they will be screened for eligibility. They will be asked questions regarding the Inclusion and Exclusion criteria. If the child is determined eligible, we will schedule their first session, which will start with debriefing about the purposes of the study, benefits and risks. After debriefing, participants will sign the Informed Consent (if they are still willing to participate), and proceed to the study. (Please see attached script for eligibility screening and obtaining Informed Consent).

Withdrawal from the Study

Each participant (and their parents) has a right to withdraw from the study at any time. If a participant decides to withdraw from all components of a research study, we will discontinue interacting or intervening with the participant in order to obtain data about his or her participation in the study, we will not obtain additional identifiable private information about the participant for the research study from any source, and we will not obtain identifiable private information about the participant for the research study by observing or recording private behavior without interacting with the participant.

When a participant will inform us that he / she decides to withdraw, we will ask the participant to clarify whether the participant wishes to withdraw from all components of the trial or only from the primary interventional component of the trial. If the participant wishes to withdraw only from the primary interventional component, we may ask for permission to contact the participant to collect follow-up data about the child's behavior.

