9.0 Recommendation for Only One Parent Consent

Both this proposed study and the investigational device do not involve greater than minimal risk.

Rationale for the device:

Safety of Photobiomodulation: Photobiomodulation has been extensively studied on humans for more than 30 years, including its use for neurological conditions. There are several photobiomodulation products (for neurological conditions) that are on currently on the market (using both LED and Lasers). The consumers report no side-effects.

After more than three decades of research there are no known major side effects attached to photobiomodulation therapy.

Rare Minor Side effects for first time users only include: Tiredness (temporary) – probably due to the release of metabolites but the majority report a resurgence of energy. Headaches (temporary) – from the reactivation of neural connections and increased microcirculation.

Safety Issues of our product specifically: Our product emits non-laser based irradiation (incoherent light) with a low level energy intensity. Infrared emits non-laser based irradiation (incoherent light) with a low level energy intensity. We use 850 nm. The participants might perceive slight warm. No other perceptions will be produced by wearing the device. No feelings of discomfort are anticipated (the device is especially made for children, it's very comfortable and soothing to wear). There are no known side-effects of photobiomodulation (with 30 years of research and studies, including research on 5 year old children diagnosed with ASD).

Rationale for the study:

The study activities include: 1) wearing the device and / or 2) Listening to the audio program which provides language acquisition input or 3) free play while listening to nursery rhymes. In addition, the parents will be interviewed about the child's behavior on a weekly basis.

None of these activities present greater than minimal risk to the health and well-being of the participants.

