The participants will be explained that they can refuse to answer any question. They can also refuse to participate in the study at any time. We do not anticipate uncomfortable questions, however, we will assure the participants that their level of comfort is of utmost importance, and we will explain to them that there is no penalty involved for their refusal to answer any specific question.

Only [name] and [name] will be able to access individual information. The participants will be immediately assigned Study ID number and only STUDY ID will be used for data analysis and reporting. Only aggregated data will be used for further reporting to the scientific community or to the business community. Individual data will be reported for illustrative purposes only with STUDY ID (not identifying personal information).

The following information will be included as data: Signed consent form (immediately scanned and stored in a cloud). Pre and Post-test Cars2 scores (with STUDY ID assigned). Weekly interview data (with STUDY ID assigned).

Identifying information will include Name and Age, Gender and number of therapy hours of the participant, Name and phone number of the parent. Children's age, gender and number of therapy hours will be used for matching purposes (for assigning to the control or treatment condition). Neither names of the participants nor names and phone numbers of their parents will be used for data analysis or reporting. Their names and phone numbers will be stored separately, in encrypted (password protected) file, in a secure cloud. Secure clouds as well as encryption and password protection will be used to protect identifying information.

The raw research data will be stored for 6 years. The identifying parental information will be kept for a year, for potential follow up interviews. The consent form will include their permission to keep identifying data for a year.

Although we do not plan to re-contact the participants after the study is complete, a follow up interview in 6 months or a year could be useful to assess the sustainability of the benefits of photobiomodulation. In this case, we will be applying for a separate IRB (minimal risks) to conduct the follow up interview. Presently, we do not plan to do it (although we recognize that it could potentially be useful for research purposes).

The data will be stored in encrypted, password protected files in a secure cloud.

15.0 Data Monitoring Plan to Ensure the Safety of Participants:

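### Section 4.0 promises to control for behavioural therapy, but no stated model contains a therapy term and no listed record captures how much therapy children receive after entry

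*Protocol*

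**What the plan says.** **Therapy.** Protocol section 4.0, inclusion criterion 3, states "Participants may be receiving any behavioral intervention therapy (e.g., ABA, Floor Time) during the course of the treatment". It expects most children in both arms to be receiving therapy and adds: "The final statistical analysis will control for the participants receiving behavioral therapies in control and experimental conditions". Nothing requires therapy to stay stable.

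**What is recorded.** Section 7.3 says "The participants will be matched on age, gender and number of hours of therapy they receive independent from the study". Section 14.0 gives the same use: "Children's age, gender and number of therapy hours will be used for matching purposes". The daily diary in section 7.7 covers "words spoken, comprehension of instructions, eye contact, his sleep pattern, number of tantrums, anxiety, social interaction and eating", and the weekly interview covers similar ground. The table in section 13.0 adds that staff will follow, from interviews and diaries, how well the child works with and benefits from ABA.

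**Medication.** Section 4.0 excludes a child if "Participant has receiving medication on a regular basis for Autism or any other medical condition", and separately excludes current psychotropic treatment. Section 13.0 places this check at initial screening. Neither document mentions medication started later.

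**Analysis.** Section 7.7 names a mixed-design ANOVA of total CARS2 scores. The SAP (Primary Analyses) names an independent-samples t-test on change from baseline. Neither lists a covariate. The SAP compares treatment status between arms under Baseline Data only.

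**The concern.** There are two linked gaps.

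First, the protocol makes an explicit analytic promise that does not appear in either stated model.

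Second, even if the promise were kept with the one therapy quantity described, that quantity is an entry value. Randomisation protects against imbalance in entry therapy on average. It does not govern what families do afterwards. Caregivers attend every session, and the arms differ in ways a parent could notice: lights on or off, and nursery rhymes in the placebo arm against the audio program in the treatment arm. Section 13.0 itself foresees that a parent may be upset if a placebo child does not improve. Parents could respond by adding, dropping or changing therapy at different rates in the two arms. If so, part of the CARS contrast would reflect co-treatment, and the listed records would not show how much.

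**Working it through.** **1. The promise against the plan**

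| What control for therapy needs | What the documents give |
|---|---|
| A therapy term in the model | None in the section 7.7 ANOVA; none in the SAP t-test |
| Entry therapy hours | Described in 7.3 and 14.0, for matching only |
| Matching built into allocation | 7.4 alternates arms down a random list and does not use hours |
| Therapy amount after entry | Not among the listed diary or interview topics |
| Response to ABA after entry | Yes (13.0), but this is response, not amount |
| Medication started after entry | Not addressed |

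**2. Reproducing the reported result (SAP, Primary Outcome)**

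- Difference in mean change: (43.5 − 33.7) − (40.6 − 38.0) = 9.8 − 2.6 = 7.2, against 7.23 stated.
- CI half-width: (12.107 − 2.357) / 2 = 4.875.
- With n = 16 and 14 (28 df), SE = 4.875 / t(0.975, 28) = 2.38.
- t = 7.232 / 2.38 = 3.04, p = 0.005, consistent with the stated 0.01 after rounding.
- Implied SD of change: 2.38 / √(1/16 + 1/14) = 6.50.

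The result reproduces. It can serve as the reference for a sensitivity calculation.

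**3. How large a bias might be (assumed inputs)**

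The documents give no figure for co-treatment change or its effect on CARS. Take bias = (between-arm difference in the share of families who change co-treatment) × (CARS points per change).

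- Low: 0.10 × 2 = 0.2 points, or 0.2 / 7.23 = 3%.
- High: 0.30 × 5 = 1.5 points, or 1.5 / 7.23 = 21%.

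The 5-point input is generous: it is nearly twice the mean sham improvement of 2.6.

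Subtract a bias B favouring active from 7.23 and hold the half-width at 4.875:

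| B | Difference | 95% CI |
|---|---|---|
| 0.2 | 7.03 | 2.16 to 11.91 |
| 1.5 | 5.73 | 0.86 to 10.61 |
| 2.0 | 5.23 | 0.36 to 10.11 |
| 2.36 | 4.87 | 0.00 to 9.75 |
| 3.0 | 4.23 | −0.64 to 9.11 |

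The threshold of about 2.36 can be expressed in therapy hours. If one extra weekly hour were worth 0.1, 0.25, 0.5 or 1.0 CARS points (assumed), the between-arm difference needed would be 2.357 divided by that value: 23.6, 9.4, 4.7 or 2.4 hours per week.

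**4. Whether entry hours can remove a later difference**

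A simulation used 2,000 runs, 15 per arm, SD 6.50 and no true effect. It assumed 0.5 points per hour and 4 extra weekly hours in the active arm after entry. The expected bias is 0.5 × 4 = 2.0.

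- Unadjusted estimate: 1.88.
- Adjusted for entry hours: 1.88.
- Adjusted for entry hours and on-study change: −0.13.

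The expected values are 2.0, 2.0 and 0; the departures are simulation error. Entry hours leave the later bias untouched. The third estimate is near zero only because, in the simulation, on-study change was not itself a response to the child's progress. In a real trial it may be, so that adjustment cannot be primary.

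**The case against.** **Medication.** A reader might infer that medication was free to change. The documents do not say so: regular and psychotropic medication are exclusions, and the promised control concerns behavioural therapy alone. What stands is the silence about medication started after entry.

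**Monitoring exists.** A reader might also infer that therapy was observed only at entry. Section 13.0 does follow response to ABA through interviews and diaries, so the diary list in 7.7 is not complete. That stands, but response is not amount.

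**Unseen material.** The weekly interview script is an attachment that was not supplied, and part of the SAP was not available. Questions on therapy, or an adjusted analysis, could sit there. The point therefore covers only the listed topics and the stated models.

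**Home light devices.** Section 9.0 says "There are several photobiomodulation products (for neurological conditions) that are on currently on the market", but as a safety argument. Nothing suggests that enrolled families used one, so this is at most an optional question.

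**Direction and purpose.** Sham families adding therapy, or active families dropping it, would shrink the contrast and make the reported benefit conservative. Usual-care changes after randomisation can also be treated as part of a treatment-policy comparison, and this is a feasibility study. Both points are fair, and they lower the stakes. They do not remove the section 4.0 promise, and even a treatment-policy result is hard to interpret without co-treatment described by arm.

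**Conclusion.** The point holds in a limited form. The promised control for behavioural therapy appears in no supplied model, and the listed records cannot show whether therapy amount or new medication came to differ by arm after entry.

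A reader might go further and infer that uneven co-treatment explains the 7.23-point difference. The documents do not support that. They do not show that any family changed co-treatment, and the direction of any bias is unknown. Across the assumed range of 0.2 to 1.5 points the interval stays above zero; about 2.36 points favouring active would be needed to bring the lower limit to zero. These figures rest on assumed shares and effects, with the standard error held fixed. They show what would matter, not what happened.

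**What to change.** 1. **Primary model.** Analyse the CARS comparison with a model that includes entry therapy hours, for example ANCOVA of post-treatment CARS on arm, baseline CARS and entry hours. This delivers the section 4.0 promise at almost no cost. Section 14.0 files hours with identifying information, so they need to be carried into the analysis dataset under the Study ID.
2. **Co-treatment log.** In both arms, record weekly therapy hours, any therapy started or stopped, and any new regular medication. An item on light devices used outside the study is optional. Under section 7.8 the blinded rater also runs the weekly interviews, and section 13.0 uses diaries for monitoring. The log should therefore be a separate sheet, collected by the treating researcher and not read by the rater. Parents could still mention changes to the rater, so this reduces the exposure without removing it.
3. **Reporting.** Tabulate the log by arm. Use on-study change only in a sensitivity analysis labelled as post-randomisation. Keep all randomised children in the primary analysis; do not rely on dropping those whose co-treatment changed, because that selects on something that may follow from the child's progress.
4. **Data already reported.** A new log cannot recover them. Tabulate any available co-treatment information by arm, or state the gap as a limitation.

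The cost is one short sheet, one table and one sensitivity analysis, with slightly more burden for parents.
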